2.5 Determination of Sample Size

No formal calculations were performed to determine sample size for this study. The sample size is based on feasibility and is similar to that of comparable studies.

A total of 24 subjects will be enrolled: 12 non-Hispanic, Caucasian subjects and 12 subjects of Japanese descent (1:1 male: female). Non-Hispanic, Caucasian subjects will be matched to Japanese subjects based on sex, age (± 7 years), and body mass index ($\pm 15\%$).

2.6 Multiplicity Adjustments for Type I Error Control

Not applicable, as the statistical analyses are for exploratory rather than confirmatory purposes.

3. OBJECTIVES

3.1 Primary Objective

- To compare the PK profile of recombinant human parathyroid hormone (rhPTH[1-84]), administered as a single SC dose of 100 μ g, between healthy adult volunteer subjects of Japanese descent and matched, non-Hispanic, healthy, adult Caucasian subjects.

3.2 Secondary Objectives

- To assess the dose proportionality of the selected PK parameters of rhPTH(1-84) in healthy adult volunteer subjects of Japanese descent when exposed to single SC doses of rhPTH(1-84) at 25 μ g, 50 μ g, and 100 μ g.
- To compare the PD profile (serum calcium and phosphate concentration levels vs time) of a 100 μ g SC injection of rhPTH(1-84) in healthy adult volunteer subjects of Japanese descent and matched, non- Hispanic, healthy, adult Caucasian, subjects.
- To assess the PD profile (serum calcium and phosphate concentration levels vs time) of a 25 μ g and 50 μ g SC injection of rhPTH(1-84) in healthy adult volunteer subjects of Japanese descent.
- To assess the safety and tolerability of single SC doses of 25 μ g, 50 μ g, and 100 μ g of rhPTH(1-84) in healthy adult volunteer subjects of Japanese descent.
- To evaluate the safety and tolerability of a 100 μ g SC injection of rhPTH(1-84) in matched, non-Hispanic, healthy, adult volunteer Caucasian subjects.

3.3 Exploratory Objective

- To evaluate the PK similarity of rhPTH(1-84) administered as a single SC dose at 25 μ g and 50 μ g between healthy adult volunteer subjects of Japanese descent and matched, non-Hispanic, healthy, adult Caucasian subjects using dose-normalized PK data.

4. SUBJECT POPULATION SETS

4.1 Enrolled Set

The Enrolled Set consists of all subjects who sign the informed consent form and meet the study inclusion/exclusion criteria.

4.2 Safety Analysis Set

The Safety Set consists of all subjects who have received at least 1 dose of investigational product.

4.3 Pharmacokinetic Set

The Pharmacokinetic Set consists of all subjects who have received at least 1 dose of investigational product and have at least 1 evaluable post dose PK concentration value.

4.4 Pharmacodynamic Set

The Pharmacodynamic Set consists of all subjects who have received at least 1 dose of investigational product and have at least 1 evaluable post dose PD concentration value.

5. SUBJECT DISPOSITION

Final subject numbers will be presented for subjects that had been re-screened.

The number of subjects included in each subject set (i.e., Enrolled, Safety, Pharmacokinetic, and Pharmacodynamic) will be summarized by ethnic group (Japanese or Non-Hispanic Caucasian) and treatment sequence. Details of randomization assignments for randomized subjects will be listed.

Additionally, the number and percentage of subjects who either completed or prematurely discontinued during the study will be presented. Reasons for premature discontinuation from the study as recorded on the termination page of the eCRF will be summarized (number and percentage) by ethnic group and treatment sequence for the Enrolled Set. Details of reasons for discontinuation for all subjects who prematurely discontinued during the study will be listed.

For Japanese subjects, the number and percentage of subjects in each subject set, and who either completed each treatment period or prematurely discontinued during each treatment period including reasons will also be summarized by rhPTH(1-84) dose. Discontinuations will be attributed to the last dose that the subject received prior to discontinuation.

6. PROTOCOL DEVIATIONS

All protocol deviation data will be listed for the Enrolled Set.

7. DEMOGRAPHIC AND OTHER BASELINE CHARACTERISTICS

Descriptive summaries of demographic and baseline characteristics will be presented by ethnic group and treatment sequence, for the Safety Analysis Set. For Japanese subjects, demographic and baseline characteristics will also be summarized by rhPTH(1-84) dose for the Safety Analysis Set.

The following demographic characteristics will be summarized in the following order in the tables: age, sex, ethnicity and race. Other baseline characteristics including weight, height and BMI will be summarized.

BMI will be calculated locally at screening for eligibility using the formula below:

$$\text{BMI} = \frac{\text{weight [kg]}}{(\text{height [m]})^2}$$

A listing will be created to show all the demographic and baseline characteristics for the Safety Analysis Set.

Medical history will be listed for the Safety Analysis Set.

8. EXTENT OF EXPOSURE AND TREATMENT COMPLIANCE

8.1 Exposure to Investigational product

A summary table showing number of subjects exposed to each dose will be produced by visit and ethnic group for the Safety Analysis Set.

A listing will be created by subject number and visit giving the date and time of dose administration, for the Safety Analysis Set.

8.2 Measurement of Treatment Compliance

Since this is a Phase 1 study in which the study medication is administered at the Clinical Research Center (CRC), no summary of treatment compliance will be produced.

9. PRIOR AND CONCOMITANT MEDICATION

Version WHODRUG 2017MAR01 DDE (B2 format) will be used to classify prior and concomitant medications by preferred term. Medications will also be coded by the Anatomical Therapeutic Chemical (ATC) classification system.

Medications starting within 30 days before the first dose of investigational product and up to the end of the follow-up period will be collected on the CRF.

Prior medication is defined as any medication with the start date prior to the date of the first dose of investigational product. Concomitant medication is defined as any medication with a start date prior to the date of the first dose of investigational product and continuing after the first dose of investigational product or with a start date after the date of the first dose of investigational product.

Concomitant medication usage will be summarized by the number and proportion of subjects receiving each medication by preferred term, by ethnic group and rhPTH(1-84) dose for the Safety Analysis Set. Medications can be counted both as prior and concomitant medication. Multiple medication usage by a subject in the same category will be counted only once.

Concomitant medications will be assigned to the dose(s) with which they are concomitant. A medication is concomitant with a dose of rhPTH(1-84) if the subject received that medication any time between the time when that dose of rhPTH(1-84) was received and when the next dose of rhPTH(1-84) was received, or in the case of the last dose, until the end of the follow-up period. Therefore, a medication may be concomitant with more than one dose.

All prior and concomitant medication will be listed.

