5.2 Concomitant Treatment

Concomitant treatment refers to all treatment taken between the dates of the first dose of investigational product and the end of the follow-up period, inclusive. Concomitant treatment information must be recorded on the appropriate source document.

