18.5.1 Incomplete Start Date and Time

The following rules will be applied to impute the missing numerical fields. If the stop date is complete and the imputed start date is after the stop date, then the start date will be imputed using the stop date.

Missing day and month

- If the year of the incomplete start date is the same as the year of the date of the first dose of investigational product, then the day and month of the date of the first dose of investigational product will be assigned to the missing fields
- If the year of the incomplete start date is before the year of the date of the first dose of investigational product, then December 31 will be assigned to the missing fields
- If the year of the incomplete start date is after the year of the date of the first dose of investigational product, then 01 January will be assigned to the missing fields.

Missing month only

- The day will be treated as missing and both month and day will be replaced according to the above procedure.

Missing day only

- If the month and year of the incomplete start date are the same as the month and year of the date of the first dose of investigational product, then the day of the date of the first dose of investigational product will be assigned to the missing day
- If either the year is before the year of the date of the first dose of investigational product or if both years are the same but the month is before the month of the date of the first dose of investigational product, then the last day of the month will be assigned to the missing day
- If either the year is after the year of the date of the first dose of investigational product or if both years are the same but the month is after the month of the date of the first dose of investigational product, then the first day of the month will be assigned to the missing day.

Missing/Incomplete Time

- If the time is missing and the date is complete and is the same as the date of the first dose of investigational product, or the date is imputed to be this date, then the time will be set to the time of the first dose of investigational product. Otherwise, missing times will be imputed as 00:00.
- If the minutes are given but the hour is not, then the time will be regarded as completely missing and handled as above. If the hour is given but the minutes are not, then if the hour is the same as the hour of the first dose of investigational product, then the minutes of that

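### SAP 9 defines prior and concomitant medication so that a drug started on the first-dose date is neither, contrary to Protocol 5.2 and to the SAP's own per-dose rule

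*SAP*

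**What the plan says.** SAP 9 gives two definitions. For prior: "Prior medication is defined as any medication with the start date prior to the date of the first dose of investigational product". For concomitant, the first limb is "Concomitant medication is defined as any medication with a start date prior to the date of the first dose of investigational product and continuing" past the first dose, and the second limb is "or with a start date after the date of the first dose of investigational product".

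The same section then allocates drugs to doses. It opens with "Concomitant medications will be assigned to the dose(s) with which they are concomitant" and goes on to say that a drug belongs to a dose "if the subject received that medication any time between the time when that dose of rhPTH(1-84) was received and when the next dose", or until the end of follow-up for the last dose. It closes by promising a listing of all prior and concomitant medication.

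Protocol 5.2 defines concomitant treatment as "all treatment taken between the dates of the first dose of investigational product and the end of the follow-up period, inclusive".

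SAP 18.5.1 handles partial start dates. When only the day is missing and the month and year match those of the first dose, "then the day of the date of the first dose of investigational product will be assigned to the missing day". When day and month are both missing and the year matches, the first-dose day and month are used. A missing time on that date becomes the time of the first dose. If a complete stop date is earlier than the imputed start, the stop date is used instead.

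SAP 17 lists the departures from the protocol. This is not among them.

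**The concern.** Both SAP 9 definitions compare dates strictly: before, or after. Neither covers a start date equal to the first-dose date. That date is Day 1, the only dosing day for the Caucasian group and the 100 µg day for everyone. Protocol 3.2 puts the PTH peaks at about 0.5 hour and 2-3 hours, with a return to baseline at about 12 hours. A drug given for an acute effect of 100 µg would therefore most naturally start on the date that the definition leaves out.

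At stake is the descriptive record of medication use at 100 µg: Table 1.3.1 (concomitant medication by ethnic group and dose) and Listing 4.4. There is also a mismatch with the adverse event tables. SAP 11.1 treats an event as treatment-emergent if it starts at or after the first dose, so a headache two hours after the Day 1 dose would be tabulated under 100 µg while the drug given for it that day would not meet the definition of concomitant.

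**Working it through.** The plan gives no figure to reproduce. The check applies each rule to the same set of records.

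**Rules.** Let S be the start, E the stop, and F the first dose.

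- SAP 9 prior: date(S) < date(F).
- SAP 9 concomitant: date(S) < date(F) and E after F, or date(S) > date(F).
- Protocol 5.2: any treatment taken on or after date(F), up to the end of follow-up.
- SAP 9 per-dose rule read alone: any treatment taken at or after the time of F.
- SAP 18.5.1: partial start dates imputed as described above.

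**Assumption.** F is set at 15 May 2017, 08:00, for illustration. The pattern does not depend on this choice.

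| Record | SAP 9 definitions | Concomitant under Protocol 5.2? | Counted by per-dose rule alone? |
|---|---|---|---|
| 1. Started Day -1, continued to Day 6 | prior and concomitant | yes | yes |
| 2. Started Day -1, stopped before the dose | prior | no | no |
| 3. Day 1, single use 2 h before the dose | **neither** | yes | no |
| 4. Day 1, single use 3 h after the dose | **neither** | yes | yes |
| 5. Day 1, started 3 h after the dose, continued to Day 6 | **neither** | yes | yes |
| 6. Day 2 | concomitant | yes | yes |
| 7. Day unknown, dosing month, stopped Day 6 | **neither** (imputed to F) | yes | yes |
| 8. Day and month unknown, dosing year, stopped Day 6 | **neither** (imputed to F) | yes | yes |
| 9. Day unknown, dosing month, stopped before Day 1 | prior (start reset to stop date) | no | no |
| 10. Day unknown, month before dosing, stopped Day 6 | prior and concomitant | yes | yes |

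**Reading the table.** Five of the ten test records (3, 4, 5, 7, 8) fall in neither SAP 9 class. Protocol 5.2 counts all five as concomitant, and the per-dose rule read alone counts four of them. Records 4 and 6 are the same kind of use one day apart, and only the later one is classified. Record 9 shows the limit of the imputation problem: an earlier complete stop date moves the start back, so only records whose final imputed start is the first-dose date are caught.

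**Columns affected.** A drug first given on Day 4 or Day 7 starts after date(F) and is counted under 25 or 50 µg. The same drug first given after the Day 1 dose is not counted under 100 µg. Record 5 would also be missing from the Day 4 dose column, although the drug was still in use then.

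**Scale.** With 12 subjects per group, one omitted subject is 1/12 = 8.3 percentage points of a 100 µg column. This is the weight of one record, not an estimated effect; the documents give no rate of Day 1 medication use.

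**The case against.** The best defence lies in SAP 9 itself. The per-dose sentence speaks of a medication in general, works by clock time, and governs the columns of a table organised by dose. A programmer who followed it alone would put a drug given three hours after the Day 1 dose under 100 µg. Protocol 5.2 points the same way, and the SAP presents itself as an elaboration of the protocol, so the definition looks like a slip for on-or-after. This part stands: loss of the Day 1 drugs is not certain. It does not remove the conflict, because the sentence before it applies the per-dose rule to drugs already classed as concomitant. One section then supports two different programs.

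A reader might infer a bias in the ethnic comparison. The documents do not support that. Both groups receive 100 µg on Day 1, so the same rule acts on both 100 µg columns. The planned comparison is of PK parameters by Welch's t-test and uses no medication data. The asymmetry that remains is 100 µg against 25 and 50 µg within the Japanese group, in a table with no planned test.

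A reader might also picture a stream of rescue treatment being lost. The documents use no such term. Protocol 5.2.1 asks subjects to avoid medication, with listed exceptions (among them occasional NSAID use) and the investigator's discretion for safety. These are healthy volunteers confined from Day -1, so Day 1 drugs should be few and rarely have partial dates. The data themselves are safe: SAP 9 has medications collected on the CRF from 30 days before the first dose to the end of follow-up, and reclassification stays possible.

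**Conclusion.** The gap is real on the plain wording. A medication that starts on the first-dose date is neither prior nor concomitant under SAP 9, in conflict with Protocol 5.2 and with the per-dose rule in the same section, and SAP 17 does not declare it. Records whose final imputed start is that date share the gap.

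The consequence is conditional. If the definition is used as a filter, post-dose Day 1 drugs leave Table 1.3.1 and Listing 4.4 for 100 µg in both ethnic groups. If the per-dose rule is used alone, they stay. How many records this concerns cannot be derived from the documents. No PK, PD or adverse event result depends on it. It is a wrong rule in a descriptive summary, worth correcting before database lock because two competent programmers could produce different tables from the same text.

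**What to change.** In SAP 9, define both classes by date and time:

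- **Concomitant:** start on or after the date and time of the first dose, or start before it and ongoing at it.
- **Prior:** start before the date and time of the first dose.

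A drug may still be both. Records 4, 5, 7 and 8 then become concomitant, and record 3 (single use before the Day 1 dose) becomes prior. Changing the concomitant limb alone would leave record 3 unclassified. A Day 1 start with a missing time needs no extra rule, because SAP 18.5.1 already sets it to the time of the first dose.

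Protocol 5.2 works by date, so it would call record 3 concomitant. One line in SAP 17 should note that small difference.

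The cost is a short text edit and the matching program condition. No new data are needed.

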10. EFFICACY ANALYSES

No efficacy analysis will be performed for this study.

10.1 Primary Efficacy Endpoint(s) and Analysis

Not applicable.

10.2 Key Secondary Efficacy Endpoint(s) and Analysis

Not applicable.

10.3 Other Secondary Efficacy Endpoint(s) and Analysis

Not applicable.

10.4 Exploratory Efficacy Endpoint(s) and Analyses

Not applicable.

11. SAFETY ANALYSES

The safety analysis will be performed using the Safety Analysis Set. Safety variables include AEs and TEAEs, clinical laboratory variables, vital signs, and ECG variables. For clinical laboratory and vital sign variables, the last value collected before the dose administration will be used as baseline for all analyses of that safety variable in the respective dose interval. Thus there will be a different baseline for each dose for the Japanese subjects.

Follow-up visits will be summarized under the 100 μ g dose, regardless of which sequence the subject was randomized to, or which doses they had received.

